#### 4) Study Design and Methods:

##### a) Study overview

This is an out-patient study lasting approximately 5-7 months. Subjects will be asked to make visits to the clinic every one to two weeks. Each visit will last up to two hours. In addition, some subjects will complete additional procedures such as PET or fMRI scans for which there are separate consents.

b) Recruitment

Recruitment Screening Methods

Participants will be sought by advertising for women who do not experience menstrually-related mood disturbances.

- Flyers will be produced with tear-offs. Posters will not have tear-offs.
- Flyers/poster will be used in color as submitted, or may be printed in black and white. Color changes to recruitment material will be made proportionately throughout and will not be used to change the emphasis of the material.
- The size of the flyers/posters/ads may vary, but all parts, including fonts and pictures, will be changed proportionately. Disproportionate changes in size will not be used to change the emphasis of the material.
- The size of the flyers/posters may vary, but all parts, including fonts and pictures, will be changed proportionately to the rest of that flyer. Disproportionate changes in size will not be used to change the emphasis of the flyer.
- Flyers/posters may be posted on bulletin boards on the NIH campus, and at coffee shops, grocery stores, bookstores, libraries, fitness centers, community centers, or placed in venues, such as at advocacy group offices, in doctor's office waiting rooms, and retail establishments with approval of the venue or in accord with their policy.

- Flyers/posters may be made available at outreach exhibits, speaking engagements, support group meetings, parenting groups, professional meetings, and association/trade meetings with approval of the venue or in accord with their policy.
- Flyers/posters may be given directly to persons requesting study information.
- Flyers/posters may be posted electronically on websites such as NIH or NIMH websites, advocacy/parenting group websites such as PTAs, athletic groups or neighborhood groups, publications' websites such as Washington Parent, or Gazette.
- Flyers/posters may be sent electronically to persons requesting study information
- Flyers/posters may be sent electronically to listserv administrators. SBE will not post directly to listservs. Rather, an email with the material attached, including the following statement will be sent to the administrator of the listserv:

*You are receiving the email because your email address is included on this listserv. The purpose of this message is to inform you of an NIMH study that is recruiting subjects. The administrator of this listserv has permitted its use for this distribution.*

The administrator has the option of sharing the information with their list. Examples of types of listservs to be contacted include professional groups, parenting/ family, school, sport groups, women's health and fitness. SBE will retain copies of all correspondence with the administrator of each listserv and submit as requested to the IRB.

- IRB-approved advertisements may be placed in local and national print publications of newspapers, magazines and support or health care organizations, such as The Washington Post, The Express, Washington Parent, Gazette, Washingtonian, Washington Jewish Week and others.
- NIH Record announcements will appear as text in the NIH Record.

c) Screening

Subjects are initially screened for this protocol via participation in screening protocol 81-M-0126. All subjects will have a two month baseline screening period during which mood and behavioral ratings will be obtained. The absence of menstrual-related mood disorders will be prospectively confirmed during a two month period prior to the study entry when subjects will complete daily visual analogue rating scales monitoring both mood and behavior as outlined in NIMH protocol # 81-M-0126.

The Structured Clinical Interview for DSM-IV (130) will be administered to controls prior to study entry. Any control with a current or past axis I psychiatric diagnosis will be excluded from participating in this protocol (except in the subgroup of asymptomatic women with a past major depressive episode who participate in this protocol).

Prior to treatment, a complete physical and neurological examination will have been performed and the following routine laboratory data obtained:

A. Blood

Complete blood count; thyroid function tests; cortisol; renal function tests, such as BUN and creatinine; electrolytes; glucose; liver function tests, B-hCG for pregnancy test.

B. Urine

Routine urinalysis.

GnRH agonist will not be administered to any subject with significant clinical or laboratory abnormalities.

Additional tests.

Results of Pap smear performed not longer than 12 months prior to onset of treatment will be obtained.

d) Study Procedures

Medications:

Following the baseline screening period, subjects will be administered 3.75 mg of GnRH agonist via intramuscular injection on a monthly basis in our clinic for a maximum of 24 weeks (see Figure I).

After week eight of GnRH agonist treatment participants will be randomized to either Group # 1 or # 2 and receive, in a sequential fashion, estradiol and progesterone as follows. The subjects who elect to participate in the brain imaging studies will receive three months of Lupron alone (rather than two) to permit their data to be compared with those from protocol # 90-M-0088. Consequently, subjects in the brain imaging studies will be randomized to Groups 1 or 2 after week 12 of Lupron alone.

Group # 1: (Figure 1) While continuing on the GnRH agonist, subjects will be administered 0.1 mg/day of 17 $\beta$ -estradiol once or twice a day via vaginal suppository for a period of five weeks. After the fourth week, progesterone suppositories (200 mg BID) will be added to provide progesterone withdrawal induced shedding of the endometrium and menses in order to prevent any effects on the endometrium of prolonged exposure to unopposed estrogen. After the four weeks of estradiol administration and the one week of combined estradiol and progesterone, there will be a two week washout period when neither estradiol nor progesterone will be given.

Subjects will then be administered progesterone suppositories (200 mg) twice daily for a period of five weeks after which no progesterone will be taken.

Group # 2: Group # 2 is identical to Group # 1 except that the order of estradiol and progesterone treatments will be reversed: progesterone suppositories (200 mg) will be administered twice daily for the first five weeks, and after a two week washout period estradiol suppositories will be administered for five weeks and in combination with progesterone during the fifth week.

Symptom Ratings:

Subjects will fill out the following symptom rating scales: (1) Self-ratings: daily ratings include a visual analogue scale (VAS) measuring the reported severity of 15 mood and behavioral symptoms, and the Daily Rating Form (131) (modified to include selected items from the DRSP (132)), which measures the severity of 15 mood and behavioral symptoms and functional impairment; biweekly clinic ratings include the Beck Depression Inventory (BDI) (133), the rating scale for Premenstrual Tension Syndrome (PMTS) – self (134), a self rating scale measuring the severity of mood and behavior symptoms, and a side effect checklist; the Derogatis Inventory of Sexual Function (135), which measures sexual interest and function, will be completed at baseline and during weeks 10-12, 14-16, and 21-23; (2) Observer ratings: the PMTS-rater form (134) will be completed during biweekly clinic visits. Symptom ratings, diagnostic interviews, and other questionnaires will be collected through an online system using a subject-specific log in and password to protect confidentiality (see Appendix I). Both participants and investigators will input data into CTDB/CTSS. Participant entered data will be reviewed during the clinic visit.

Blood Samples - After the administration of the GnRH agonist, in addition to the completion of daily mood and behavioral rating scales, blood samples (50 ml) will be drawn at

each visit, if possible, for the duration of the study (20-24 weeks). Total blood volume will be 550-660 ml. All blood sampling will be obtained in the following fashion. Subjects will arrive at the 4th or 9th floor outpatient clinic between 7:30 and 9:00 a.m.; they will be seated or placed at bed rest, a scalp vein needle will be placed in the forearm or hand via venipuncture, and approximately 50 ml of blood will be drawn. This blood will then be analyzed for several measures such as gonadotropins, estradiol, progesterone, (and its neurosteroid metabolites). Additionally, blood samples and skin biopsies (in combination with those obtained in protocol # 90-M-0088) will be analyzed for hormone and metabolic measures (as well as cellular function of the induced pluripotent cells from the skin fibroblasts taken by biopsy or peripheral blood T lymphocytes) that could distinguish either the symptomatic state in women with PMD or women with from those without PMD. In order to assess the effects of suppression of the hypothalamic pituitary gonadal axis and the re-introduction of (exogenous) estradiol and/or progesterone on cognitive function, subjects will be administered a series of cognitive test batteries at baseline, during the second month of depot Lupron treatment, and during the third weeks of both E2 and progesterone replacement. Further, subjects will be approached for their consent to participate in a number of related protocols attempting to assess and investigate the central nervous system effects of hypothalamic pituitary ovarian axis suppression as well as the effects of selective re-introduction of estradiol and/or progesterone. Related projects will include measures of regional cerebral blood flow, O  water PET, BOLD signal (protocol # 90-CC-0014), lymphoblastoid cells, and induced-pluripotent cells.

Additional Procedures:

A. Skin Fibroblasts and Peripheral Blood Cells for Induced Pluripotent Cell Studies

We wish to perform skin biopsies and collect an additional sample of venous blood in

women who have participated (or who currently are participating) in protocols 90-M-0088, titled “The treatment of menstrually-related mood disorders with the gonadotropin releasing hormone (GnRH) agonist, depot leuprolide acetate (Lupron),” and 92-M-0174, titled “The central nervous system effects of pharmacologically induced hypogonadotropic hypogonadism with and without estrogen and progesterone replacement.” Previous findings from these protocols have demonstrated a differential behavioral response (i.e., a recurrence of typical mood and behavioral symptoms experienced premenstrually) to physiologic levels of the ovarian steroids estradiol and progesterone in women with premenstrual dysphoria (PMD) compared with asymptomatic controls. The observed differential response appears to be tissue specific (i.e., neuronal) since the effects of ovarian steroids at several other target tissues does not differ in women with and without PMD (e.g., endometrium, pituitary, breast). The biological basis for this differential behavioral response to ostensibly the same physiologic stimulus is unclear; however, it is well established that tissue specificity in the response to sex steroids is mediated by factors at the level of cellular function. Receptors for both estradiol and progesterone are widely distributed throughout the brain, and recent neuroimaging studies have demonstrated that both estradiol and progesterone regulate the activation patterns in brain regions involved with the processes of affective adaptation and stress responsivity.

We hypothesize that the capacity for phenotypic differences between women with and those without PMD will be preserved in the cellular function of induced pluripotential cells (IPCs). Although the phenotypic difference in response to sex steroids is tissue specific, the latent capacity for differential expression in response to steroids should be preserved in IPCs and expressed in the differentiation of the IPCs into neural elements. Thus, we plan to obtain fibroblasts from skin biopsies and T-lymphocytes from peripheral blood (136) in order to convert

these cells into IPCs to establish neuronal and glial cell lines in both women with PMD and controls. This study will be done in collaboration with [name] at the NIAAA. The goal of this project will be to develop neurons and glial cells from participants and to characterize their gene expression patterns, morphological properties, and cell signaling pathways in response to exposures to physiologic levels of estradiol and progesterone. These experiments, therefore, will allow us to evaluate the nature of the differential behavioral response by examining protein expression and changes in cellular behaviors associated with the exposure to physiologic levels of either estradiol or progesterone across the two different behavioral phenotypes. The two behavioral phenotypes will be constituted by those women with PMD whose symptoms remit during ovarian suppression and whose symptoms recur during physiologic addback of either estradiol or progesterone. This assures the phenotypic fidelity of the subjects and avoids the false positives that would otherwise be generated if diagnoses are established solely on the basis of baseline behavioral ratings. The selection of each woman will occur after completion of the six month study to ensure both the proper characterization of the behavioral phenotype and to include comparable numbers of women in whom symptoms recur after estradiol and progesterone exposure. To recruit sufficient numbers of women in each group we will contact women who have previously participated in these protocols, have met our baseline criteria for PMD or asymptomatic controls, and have further demonstrated either the elimination of symptoms during GnRH agonist and return of symptoms upon re-exposure to estradiol or progesterone (PMD) or the absence of negative behavioral symptoms during both GnRH agonist and ovarian steroid addback phases (controls). Each of these women who is interested in participating will be re-consented for this study.

We hypothesize that the skin biopsy of the fibroblasts and the T-lymphocytes obtained

from women with PMD and those from asymptomatic controls can be converted into IPCs and differentiated into model neuronal and glial cell lines. The production of these pluripotential cell lines will retain genetic (or epigenetic) variations that will help us understand the differential behavioral response at a cellular level in this condition.

Women who participate in these protocols will be approached to obtain consent for the skin biopsies as part of the core consent documents. Additionally, we wish to contact women who have previously participated in this study in order to obtain their consent to perform a skin biopsy. Previous participants will be asked to provide consent using the new consent form accompanying this amendment. All women will be asked to provide a skin sample to study functional genomics of neuronal and glial precursors. Skin biopsies will be performed using an instrument that cuts out one or two 4 mm cylindrical pieces of skin. These biopsies are performed under local anesthesia (2% Lidocaine with or without epinephrine). The level of discomfort associated with the anesthesia is analogous to a PPD skin test for tuberculosis (TB). The biopsy itself is painless. This type of biopsy site usually heals by secondary intention and is covered with a steri-strip type bandage. If necessary, it will be closed with 1 or 2 non-absorbable sutures. These sutures can be removed by the investigator or his/her assistant, in about 7 to 10 days. No more than two biopsies will be taken at any one time. Samples derived from biopsies may be utilized for procedures such as special stains, immunohistochemistry, direct immunofluorescence or immunoelectron-microscopy for localization of immune deposits, PCR, or establishment of cell cultures. In our protocol, the samples will be used to isolate fibroblasts to grow a pluripotent cell lines.

If we are unable to produce cell lines from the initial skin sample obtained then participants will be re-contacted to allow us to take additional samples from a different area of the skin. The

repeat sample will be obtained under the same conditions as those employed to obtain the first biopsy but from a different area of the body. Risks and potential adverse reactions from a second skin sample should be similar to those of the initial sample.

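### One list of weeks for the sexual-function inventory cannot fit both the 20-week and the 24-week schedule

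*Combined protocol and SAP*

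**What the plan says.** All references are to the combined protocol and SAP.

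- **Section 4d, Symptom Ratings.** The sexual-function inventory "will be completed at baseline and during weeks 10-12, 14-16, and 21-23". The instruction is to subjects in general. No second list is given, and the week from which these numbers count is not stated.
- **Section 4d, Medications.** By default, "After week eight of GnRH agonist treatment participants will be randomized to either Group # 1 or # 2". Women who elect imaging have a longer lead-in: "subjects in the brain imaging studies will be randomized to Groups 1 or 2 after week 12 of Lupron alone". Both groups then take one hormone for five weeks, have a break in which "there will be a two week washout period when neither estradiol nor progesterone will be given", and take the other hormone for five weeks. Group 2 reverses the order with the same block lengths.
- **Section 4d, Blood Samples.** Sampling runs "for the duration of the study (20-24 weeks"), which keeps both lengths. The same paragraph times the cognitive battery mainly by treatment phase: baseline, then "during the second month of depot Lupron treatment, and during the third weeks of both E2 and progesterone replacement".
- **Section 4c, Screening.** "All subjects will have a two month baseline screening period", before any Lupron.
- **Section 9, Outcome Measures.** The symptom ratings are to be used to evaluate hypogonadism and the replacement of each hormone.

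The gel pilot has its own eight-week course and is left aside here.

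**The concern.** The inventory is informative only if each form can be tied to a hormone state: Lupron alone, estradiol or progesterone. A fixed list of weeks does that only when all women reach each state in the same weeks. The two lead-ins differ by four weeks and each window is three weeks long, so a list that suits one schedule is likely to miss on the other.

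Followed as written, the same nominal window would capture different hormone states in imaging and non-imaging women. Pooling forms by week number would then mix those states. Women on the shorter schedule would also be asked for a form after their last hormone block had ended.

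**Working it through.** **Inputs (section 4d).** Lead-in 8 or 12 weeks; first hormone (H1) 5 weeks; washout 2 weeks; second hormone (H2) 5 weeks; inventory windows 10-12, 14-16 and 21-23.

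**Step 1: reproduce the stated duration.** Total = lead-in + 5 + 2 + 5.

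- 8 + 5 + 2 + 5 = 20 weeks
- 12 + 5 + 2 + 5 = 24 weeks

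These match the 20-24 weeks given under Blood Samples.

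**Step 2: lay out the phases, with week 1 as the first Lupron week.**

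| Schedule | Lupron alone | H1 | Washout | H2 |
|---|---|---|---|---|
| 20-week | 1-8 | 9-13 | 14-15 | 16-20 |
| 24-week | 1-12 | 13-17 | 18-19 | 20-24 |

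**Step 3: place the windows.**

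| Window | 24-week schedule | 20-week schedule |
|---|---|---|
| 10-12 | last 3 weeks of Lupron alone | H1 weeks 2-4 |
| 14-16 | H1 weeks 2-4 | washout 1, washout 2, H2 week 1 |
| 21-23 | H2 weeks 2-4 | 1-3 weeks after the last addback week |

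On the 24-week schedule all 9 listed weeks sit in a distinct, well-placed phase. On the 20-week schedule none of the 3 windows falls in the phase it occupies on the 24-week schedule. Of the 9 weeks, 0 are in pre-addback Lupron alone, 3 in H1 weeks 2-4, 2 in washout, 1 in H2 week 1 and 3 after addback. Group 1 and Group 2 give the same result because their block lengths are equal.

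**Step 4: could another week origin rescue the list?** Let numbering start s weeks before first Lupron, so that listed week k is Lupron week k - s. Require the three windows to lie wholly in Lupron alone, H1 and H2 respectively.

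20-week schedule:
- Lupron alone: 10 - s ≥ 1 and 12 - s ≤ 8, so 4 ≤ s ≤ 9
- H1: 14 - s ≥ 9 and 16 - s ≤ 13, so 3 ≤ s ≤ 5
- H2: 21 - s ≥ 16 and 23 - s ≤ 20, so 3 ≤ s ≤ 5
- All three: s = 4 or 5

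24-week schedule:
- Lupron alone: 10 - s ≥ 1 and 12 - s ≤ 12, so 0 ≤ s ≤ 9
- H1: 14 - s ≥ 13 and 16 - s ≤ 17, so -1 ≤ s ≤ 1
- H2: 21 - s ≥ 20 and 23 - s ≤ 24, so -1 ≤ s ≤ 1
- All three: s = 0 or 1

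The two sets do not overlap, so no single origin serves both schedules. Counting the two-month screening (taken as 8 weeks, s = 8) satisfies neither. Calling the first Lupron week week 0 (s = -1) also leaves the 20-week misfit: H1 weeks 3-5; washout week 2 plus H2 weeks 1-2; then 2-4 weeks after the last addback week.

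**Step 5: windows that would match on the 20-week schedule.** Moving each window four weeks earlier gives 6-8, 10-12 and 17-19. These are the last 3 weeks of Lupron alone, H1 weeks 2-4 and H2 weeks 2-4.

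**The case against.** **The 20-week group may be empty.** The payment table covers six Lupron injections and six months of ratings, the blood-drawing schedule describes a 24-week core protocol, and the standard consent is labelled six months. The Medications text also still prescribes estradiol suppositories, which section 1D says could not be used, so the week-eight lead-in may be a leftover too. This limits the importance of the point but does not settle it. The sampling duration still reads 20-24 weeks, the consent section still speaks of a five or six month trial, and the study overview says only some subjects have scans. If the 8-week lead-in is obsolete, the protocol still prescribes it.

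**The week origin is inferred.** This is correct. That the list suits the 24-week schedule depends on counting from first Lupron. That one list cannot suit both schedules does not depend on it (Step 4).

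**The comparison is not strictly lost.** A reader might infer that the inventory cannot compare the three hormone states at all in a woman on the 20-week schedule. The documents do not support that. Addback is given while Lupron continues, so a form from washout weeks 14-15 is a form on Lupron without addback, though with possible carryover. Weeks 21-23 would be the same if Lupron is given up to the stated 24-week maximum (an assumption). A form completed in week 16 is on the second hormone, although only in its first week. The comparison is badly timed and not matched to the 24-week women, but it is not impossible.

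**The consequence is small.** The inventory is not one of the numbered outcomes and plays no part in the sample size. The daily and biweekly ratings and the phase-timed cognitive battery are unaffected. Nothing says the analysis will go by nominal week. All of this stands.

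**Conclusion.** The point holds as an internal inconsistency in section 4d: two schedules and one list of inventory weeks that no single numbering can fit to both.

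With weeks counted from first Lupron, a woman on the 20-week schedule has no pre-addback Lupron-alone form and at most a very early second-hormone form (week 1, or weeks 1-2 if numbering starts at 0). Her only forms without addback come from washout or after the last block. She therefore lacks forms that are phase-matched to those of the 24-week women.

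The size is modest. One secondary inventory is affected, in a group whose number is not stated and may be zero, so no share of the sample can be given. The figure and the flow sheet are not shown in the text reviewed and might set out visit timing more fully; the conclusion concerns the written text only. It is worth correcting because the correction is cheap.

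**What to change.** Reconcile the Medications and Symptom Ratings text of section 4d in one of two ways.

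1. **If both schedules are in use,** define the inventory windows by phase, as is largely done for the cognitive battery: baseline, the last 3 weeks of Lupron alone, and weeks 2-4 of each hormone. That means weeks 6-8, 10-12 and 17-19 on the 20-week schedule and the present weeks on the 24-week schedule. State that weeks count from first Lupron.
2. **If every woman now follows the 24-week schedule,** say so in both places.

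For forms already collected, assign each to the hormone phase on its completion date, using the woman's own sequence. Keep washout and post-addback forms separate from estradiol and progesterone forms. Report how many women on each schedule have a form in each phase.

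The cost is a short protocol edit and a recode by completion date, with no added questionnaires. There is one small drawback: the Lupron-alone window would fall at weeks 6-8 on one schedule and weeks 10-12 on the other, so time on Lupron differs. The analysis should note this or adjust for schedule.
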